5.1 Randomization

All patients will be randomized using the study electronic data capture (EDC) system. Patients will be randomized to treatment in a 1:1 allocation ratio using a simple randomization scheme.

5.2 Blinding

This study will be unblinded. Blinding would add substantial additional complexity without commensurate incremental benefit related to testing the primary hypothesis of a treatment strategy trial.

5.3 Patient Safety and Concomitant Therapies

This study will evaluate and compare treatment strategies of standard care and standard care + antimicrobial therapy in patients with IPF.

Although investigators are encouraged to follow the assigned treatment strategy for the study duration, in all cases the patient’s safety based on the clinical judgment of the treating physician will take priority over the specific treatment assignment.

There is the potential of adverse cardiovascular events secondary to co-trimoxazole therapy; this is felt to possibly reflect a drug interaction with trimethoprim resulting in hyperkalemia^{8,9}. Review of older literature suggests that the major risk factors for trimethoprim related hyperkalemia are higher trimethoprim dose and renal insufficiency with hypoaldosteronism, and potassium altering medications and age as probable risk factors¹⁰. Our inclusion/exclusion criteria should mitigate this risk as will monitoring for hyperkalemia early after the introduction of co-trimoxazole therapy¹⁰.

If a subject randomized to the antimicrobial strategy group develops an intolerance to co-trimoxazole the dosage should first be decreased to one double strength 160mg trimethoprim/800mg sulfamethoxazole (co-trimoxazole) three times weekly plus folic acid 5 mg daily. If intolerance continues with co-trimoxazole then the antimicrobial agent can be changed to doxycycline (with no 5mg folic acid).

Doxycycline will be dosed at 100 mg once daily if body weight is < 50 kg and 100 mg twice daily if \geq 50 kg, and no 5mg folic acid will be prescribed.

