1. EXECUTIVE SUMMARY

Title:	Study of Clinical Efficacy of Antimicrobial Therapy Strategy Using Pragmatic Design in Idiopathic Pulmonary Fibrosis (CleanUP-IPF)
Location:	Approximately 30-40 clinical sites in the United States
Objectives:	To compare the impact of an antimicrobial therapy strategy on clinical outcomes (hospitalization or death)
Study Design:	500-patient, randomized, un-blinded, phase III, multicenter clinical trial of an antimicrobial therapy strategy in idiopathic pulmonary fibrosis patients
Treatment Regimens:	
1:1 randomization to either oral antibiotic (co-trimoxazole or doxycycline) in addition to standard-of-care or standard-of-care alone.
 
The subject randomized to antimicrobial therapy will be treated with trimethoprim 160mg/800mg sulfamethoxazole (double strength co-trimoxazole) twice a day plus folic acid 5 mg daily unless there is a contraindication to this therapy.
 
If the subject develops an intolerance to co-trimoxazole the dosage can be decreased to once a day 160mg trimethoprim/800mg sulfamethoxazole (one double strength co-trimoxazole) three times weekly plus folic acid 5 mg daily.
 
If intolerance continues with co-trimoxazole then the antimicrobial agent can be changed to doxycycline (without folic acid).
 
Subjects with a contraindication to co-trimoxazole will be treated with doxycycline (without folic acid). Doxycycline will be dosed at 100 mg once daily if body weight is < 50 kg and 100 mg twice daily if \geq 50 kg.

Primary Endpoint:	Time to first non-elective, respiratory hospitalization or all-cause mortality
Secondary Endpoints:	
 • Time to death from any cause • Time to first non-elective, respiratory hospitalization • Time to first non-elective, all-cause hospitalization • Total number of non-elective respiratory hospitalizations • Total number of non-elective all-cause hospitalizations • Change in FVC from randomization to 12 months

[figure not shown]
	
• Change in DLCO from randomization to 12 months• Total respiratory infections• Change in UCSD-Shortness of Breath Questionnaire and Fatigue Severity Scale score from randomization to 12 months• Change in Leicester Cough Questionnaire score from randomization to 12 months• Change in EQ-5D score and SF-12 score from randomization to 12 months• Change in ICEpop CAPability measure for Older people (ICECAP-O) score from randomization to 12 months
--	---

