5. TREATMENT INTERVENTIONS

This will be an unblinded, randomized clinical trial comparing the following treatment strategies

- Standard care
- Standard care + oral antimicrobial therapy

Patients randomized to receive antimicrobial therapy will receive a prescription drug voucher for the medication (and folic acid if given co-trimoxazole) during the enrollment visit. To minimize risk to the participating subject and to maximize a positive outcome we have created an algorithm for antimicrobial therapy that encourages use of co-trimoxazole but allows doxycycline use.

[figure not shown]
Figure 1 illustrates the proposed antimicrobial therapy algorithm. Contraindications to co-trimoxazole at enrollment include:

- allergy to sulfa products or trimethoprim
- renal insufficiency (GFR < 30 mL/min, defined as estimated from the blood urea nitrogen and creatinine)
- hyperkalemic (potassium > 5 mEq/L)
- concomitantly taking an ACEI, ARB, potassium sparing diuretic, dofetilide, methotrexate, azathioprine, mycophenolate mofetil, cyclophosphamide
- Other contraindication to co-trimoxazole in the investigator's opinion

Subjects meeting any of the above and randomized to antibiotic therapy will take doxycycline instead. Subjects on vitamin A or retinoids will need to stop these medications if randomized to doxycycline.

Co-trimoxazole intolerance is defined by the investigator. Mild intolerance (e.g. nausea, abdominal pain, headaches, anorexia) may require a dose adjustment to half dose. Moderate intolerance (e.g. decreased leukocytes, mild increase in potassium) require a dose adjustment or a switch to doxycycline at the investigator's discretion. A significant intolerance (e.g. leukopenia, hyperkalemia, decrease in GFR by more than 50% or to less than 30 ml/min, rash) requires stopping the co-trimoxazole and providing medical treatment as appropriate. Doxycycline should be started when medically appropriate in the opinion of the investigator after moderate or significant intolerance. All dose adjustments will be at the discretion of the treating physician(s) with the medical monitor available for consultation if needed. Dosing adjustments, and/or switching of co-trimoxazole to doxycycline, will be documented within the eCRFs, as well as the reason for the adjustment.

Figure 1

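### Section 5.3's reduce-first rule for co-trimoxazole intolerance makes no exception for the significant intolerance that Section 5 says requires stopping, and the reduced dose is stated in two ways

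*Protocol*

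**What the plan says.** Protocol Section 5 (Treatment Interventions) leaves the definition of co-trimoxazole intolerance to the investigator but sorts it into three grades, each with its own action:

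- Mild: "Mild intolerance (e.g. nausea, abdominal pain, headaches, anorexia) may require a dose adjustment to half dose".
- Moderate: "Moderate intolerance (e.g. decreased leukocytes, mild increase in potassium) require a dose adjustment or a switch to doxycycline", whichever the investigator prefers.
- Significant: "A significant intolerance (e.g. leukopenia, hyperkalemia, decrease in GFR by more than 50% or to less than 30 ml/min, rash) requires stopping the co-trimoxazole" and treating the patient as needed. Doxycycline follows once the investigator considers it medically suitable.

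The same section states: "All dose adjustments will be at the discretion of the treating physician(s) with the medical monitor available for consultation if needed". Changes of dose or drug, and the reasons for them, are recorded in the eCRFs.

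Section 5.3 (Patient Safety and Concomitant Therapies) has a single ungraded instruction. On intolerance, "the dosage should first be decreased to one double strength 160mg trimethoprim/800mg sulfamethoxazole (co-trimoxazole) three times weekly plus folic acid 5 mg daily"; if the intolerance persists, doxycycline may replace it. It contains no exception and no reference back to the grades in Section 5.

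The Executive Summary gives the same step in permissive form: "the dosage can be decreased to once a day 160mg trimethoprim/800mg sulfamethoxazole (one double strength co-trimoxazole) three times weekly". Its starting regimen is "trimethoprim 160mg/800mg sulfamethoxazole (double strength co-trimoxazole) twice a day plus folic acid 5 mg daily unless there is a contraindication to this therapy". Figure 1, which sets out the treatment algorithm, is not reproduced in the text available for this review.

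**The concern.** Section 5 uses the word intolerance for all three grades, so the unqualified word in Section 5.3 takes in the significant grade as well. For a patient with hyperkalemia, a GFR below 30 mL/min or a rash, one section says stop and the other says reduce first. For a patient with moderate intolerance, one section allows an immediate switch to doxycycline and the other puts a dose reduction ahead of it. No text available says which section prevails.

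The location adds to the problem. Section 5.3 is the patient-safety section. The paragraph just before the rule names trimethoprim-related hyperkalemia as a possible mechanism for adverse cardiovascular events, and lists higher trimethoprim dose and renal insufficiency among the major risk factors. A site that turns there to decide what to do about a raised potassium finds an instruction to reduce.

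The situation is foreseeable. Section 8.1 schedules an electrolyte draw at one week for patients on co-trimoxazole, and Section 10.4 lists hyperkalemia and rash as adverse events of special interest. After the one-week draw, the next scheduled potassium is at 3 months (Section 8.3 and Appendix A), and no recheck after a dose reduction is specified in the text available.

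The second problem is separate and smaller. If half dose and three times weekly are different doses, sites could give different regimens to the same kind of patient with mild intolerance.

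**Working it through.** The plan gives no figure to reproduce here. The check sets the instructions side by side and converts the doses to weekly amounts.

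**Instructions by grade**

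| Grade (Section 5) | Action in Section 5 | Action in Section 5.3, read literally |
|---|---|---|
| Mild | May go to half dose | Reduce to 3 tablets a week |
| Moderate | Adjust dose, or switch to doxycycline | Reduce to 3 tablets a week; doxycycline only if intolerance persists |
| Significant | Stop | Reduce to 3 tablets a week; doxycycline only if intolerance persists |

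**Inputs**

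- One double-strength tablet contains 160 mg trimethoprim and 800 mg sulfamethoxazole (Executive Summary; SAP, Randomization).
- Full dose: one tablet twice daily (same places).
- Reduced dose: one tablet three times weekly (Section 5.3; Executive Summary).
- Half dose: named once in Section 5 and not defined in the text. Taken here as half of the full dose.

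**Weekly amounts**

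- Full: 2 × 7 = 14 tablets; 14 × 160 = 2,240 mg trimethoprim.
- Half: 14 / 2 = 7 tablets; 7 × 160 = 1,120 mg; 7/14 = 50% of full.
- Three times weekly: 3 tablets; 3 × 160 = 480 mg; 3/14 = 21.4% of full.

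**Differences**

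- Significant intolerance: 0 mg a week under Section 5 against 480 mg a week under Section 5.3.
- Mild intolerance: 1,120 against 480 mg a week. The difference is 640 mg and the ratio is 7/3 = 2.33.

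**Which section is out of line.** Section 5 also lists potassium above 5 mEq/L and GFR below 30 mL/min as contraindications to starting co-trimoxazole at enrollment. A rule that stops the drug when these conditions appear on treatment agrees with that list. A rule that continues it at a lower dose does not. Section 5.3 is therefore the text to change. The Executive Summary says only that the dose may be lowered, so it does not contradict a mandatory stop; it bears on the size of the reduced dose alone.

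**The case against.** The strongest reply is that Section 5.3 should not be read apart from its parent section. Section 5 is the detailed text and its stop rule is worded as a requirement, while Section 5.3 uses the weaker should. On an ordinary reading the specific requirement governs the general advice. Section 5.3 also puts the patient's safety, on the treating physician's judgment, ahead of the assigned treatment, and Section 5 leaves dose adjustments to the physician with the medical monitor available. Figure 1 may show the graded branches. On the second point, half dose may be loose shorthand for the only reduced regimen spelled out anywhere; no document prescribes 7 tablets a week.

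Much of this stands. The intended rule is not in serious doubt, a sensible clinician would probably stop the drug, and the practical harm is limited. The 7 tablets a week is an arithmetic reading of an undefined term. What Figure 1 shows cannot be judged here.

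It does not remove the conflict. The discretion clause covers dose adjustments, whereas stopping for significant intolerance is stated as a requirement. The safety clause ranks clinical judgment above the randomized assignment; it does not choose between two instructions within one arm. Even if Figure 1 follows Section 5, the sentence in Section 5.3 still disagrees with it. A stop rule should not depend on inference when one clause can settle it.

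**Conclusion.** The concern holds on both points. The main one is that Section 5.3, as written, reduces co-trimoxazole to 3 tablets (480 mg trimethoprim) a week in patients for whom Section 5 requires it to be stopped. The lesser one is that the reduced dose for mild intolerance is 50% of full dose in one place and 21% in two others, if half dose means half of the twice-daily regimen. The moderate grade may share this ambiguity, since Section 5 asks there only for an unspecified adjustment.

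This is a safety and consistency defect in the treatment instructions. It does not alter the intention-to-treat primary analysis, the sample size, power or type I error. The number of patients affected cannot be estimated from the documents. Because dose changes and their reasons go into the eCRFs, the sponsor could check what sites actually did. The conclusion rests on the text alone, without Figure 1.

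**What to change.** - **Section 5.3:** limit the reduce-first step to mild or moderate intolerance, keep Section 5's option of a direct switch to doxycycline for moderate intolerance, and add a sentence such as: for significant intolerance, stop co-trimoxazole as set out in Section 5. This is the essential change.
- **Section 5:** replace half dose with the one regimen already spelled out twice, a double-strength tablet three times weekly, once the clinical team confirms that this is what was meant.
- **Executive Summary:** the same grading could be added for consistency. This is optional, because its permissive wording does not conflict with stopping.
- **Figure 1:** check that it agrees with the corrected text.

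The cost is a protocol wording amendment and a memo to sites, with no change to design, sample size or analysis. The SAP addendum records that the trial was ended early, so the correction now matters for the protocol as written and for any reuse of this dosing algorithm.

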6. RECRUITMENT AND SCREENING PROCEDURES

6.1 Common Recruitment/Screening Procedures

All patients diagnosed at the participating centers with IPF will be screened by a study coordinator. Patients meeting eligibility criteria will be approached regarding participation in this study.

6.2 Estimated Enrollment Period

This study will enroll approximately 500 patients at 20-40 study sites. The projected enrollment timeline for enrollment is approximately 30 months.

7. SCREENING EVALUATIONS AND RANDOMIZATION

A complete schedule of assessments throughout the study is given in Appendix A.

7.1 Screening

After providing informed consent and signing the informed consent form (ICF), patients will be evaluated (via a physical examination) for eligibility into the study by ensuring that they:

- Are the appropriate age
- Have been diagnosed at the site with idiopathic pulmonary fibrosis
- Are not currently on antibiotic therapy, for treatment purposes (antibiotic prophylaxis for procedures do not meet criteria, nor do antivirals), and do not have any contraindications to antibiotic therapy.

7.2 Screening Assessments

Prior to randomization, the coordinator will document the following:

- Date of consent
- Patient characteristics (sex, race, ethnicity, age, height, weight)
- Information on how IPF diagnosis was made
- Known co-morbidities
- Details on patient history of gastroesophageal reflux disease (GERD)
- Physical exam findings
- Current concomitant medications
- Urine dipstick pregnancy test (for pre-menopausal female participants only)
- In recipients randomized to co-trimoxazole and taking digoxin, these recipients should be notified of a possible drug interaction and have additional digoxin monitoring by the provider monitoring digoxin levels for the patient.
- In recipients randomized to co-trimoxazole and taking warfarin, these recipients should be notified of a possible drug interaction and have additional coagulation (defined as PT/PTT/INR) monitoring by the provider monitoring coagulation labs for the patient.
- In recipients randomized to doxycycline and Vitamin A or retinoids, patients should be notified of a drug interaction and must stop these medications prior to starting doxycycline.
- Evaluation of seizure disorder and need for antiepileptic therapy. Antiepileptic therapy is a contraindication for enrollment.

The following procedures will be performed prior to randomization, if results are not available from recent clinically indicated testing:

- Spirometry and DLCO assessments, if not done within 90 days of randomization for clinical purposes.. The results of these tests will be recorded by the coordinator into the EDC system.
- Quality of life questionnaires
- Buccal and fecal sample collection for microbial ecology. Subjects will be given a fecal collection sample kit and instructions to take home.
- Urine pregnancy test for females who are able to become pregnant
- Blood draw for the following lab tests (**Described in Appendix B**):
 - Genotype
 - Gene expression
 - Chemistry panel and liver function tests– defined as minimum of sodium, potassium, chloride, bicarbonate, blood urea nitrogen (BUN), and creatinine, total bilirubin, direct bilirubin, alkaline phosphatase (ALP), alanine transaminase (ALT), and aspartate aminotransferase (AST)
 - Complete Blood Count (CBC)

If a subject does not meet the eligibility criteria due to a condition that subsequently resolves (e.g., infection or renal insufficiency), they may be considered for enrollment once the condition resolves if they meet the all eligibility criteria at the time of randomization.

7.3 Randomization

After providing informed consent and signing the ICF, all eligible study subjects will be randomized in a 1:1 allocation ratio to either receive or not receive a prescription drug voucher for daily antimicrobial therapy. Folic acid will also be included within the prescription drug voucher, for subjects randomized to co-trimoxazole therapy. Subjects should begin administration of drug without delay following randomization.

8. FOLLOW UP EVALUATIONS

All study participants will continue to be followed on a usual care basis. Refer to the schedule of assessments for more details. Study participants will be followed for up to a maximum of 36 months. It is anticipated that the overall study will end once the final enrolled patient completes their 12-month visit. Subjects randomized to antimicrobial therapy will remain on the assigned therapy until the end of the study or their 36-month study visit. Study participants are encouraged to contact their treating pulmonologist regarding their use of anti-microbial therapy after their study participation has ended. At the completion of the 36-month phone contact data collection will cease. To gain a better understanding of the long-term consequences of treatment, patients may be contacted up to 5 years after the end of their study participation. The primary analyses will be based on data collected until the end of the active treatment portion of the study.

8.1 One (1) week lab (Co-trimoxazole assigned subjects ONLY)

Approximately 1 week (visit window of 1 week +/- 3 days) after enrollment (and the beginning of administration of drug), subjects assigned to the antimicrobial therapy arm will return to the enrolling site or a local laboratory for the following:

- Blood drawn for electrolytes (**Described in Appendix B**)

8.2 One (1) month phone contact

Approximately 1 month (visit window of 1 month +/- 7 days) after enrollment, all subjects will be contacted by the site coordinator to document the following:

- Any issues related to drug assignment
- Vital status assessment
- Medication adherence
- Hospitalization and respiratory infection assessment

8.3 Three (3) month lab for antimicrobial assigned subjects ONLY

Approximately 3 months (visit window of 3 months +/- 7 days) after enrollment, subjects assigned to the antimicrobial therapy arm will return to the enrolling site or a local laboratory for the following:

- Blood draw for the following safety labs (**Described in Appendix B**):
 - Chemistry panel and liver function tests– defined as minimum of sodium, potassium, chloride, bicarbonate, BUN, and creatinine, total bilirubin, direct bilirubin, alkaline phosphatase, ALT, and AST
 - Complete blood count (CBC)

8.4 Six (6) month lab for antimicrobial assigned subjects ONLY

Approximately 6 months (visit window of 6 months +/- 7 days) after enrollment, subjects assigned to the antimicrobial therapy arm will return to the enrolling site or a local laboratory for the following:

- Blood drawn for the following safety labs (**Described in Appendix B**):
 - Chemistry panel and liver function tests– defined as minimum of sodium, potassium, chloride, bicarbonate, BUN, and creatinine, total bilirubin, direct bilirubin, alkaline phosphatase, ALT, and AST
 - Complete blood count (CBC)
- Vital status Assessment
- Medication adherence
- Hospitalization and respiratory infection information

8.5 Six (6) month phone contact (for standard care arm)

Approximately 6 months (visit window of 6 months +/- 4 weeks) after enrollment, subjects randomized to the standard care arm **ONLY** will be contacted by the site coordinator to document the following:

- Vital status assessment
- Medication adherence
- Hospitalization and respiratory infection information

8.6 Twelve (12) month in-person visit

All subjects will return to the enrolling site approximately 12 months (visit window of 12 months +/- 4 weeks) after enrollment and will complete the following:

- Quality-of-life questionnaires
- Spirometry and DLCO assessment
 - *If a spirometry (with DLCO) assessment is available within 90 days of the in-person visit it may be used as the study assessment. Otherwise the spirometry assessment with DLCO should be conducted at the in-person visit.
- Blood draw for the following safety labs (for antimicrobial arm only):

- Chemistry panel and liver function tests– defined as minimum of sodium, potassium, chloride, bicarbonate, BUN, and creatinine, total bilirubin, direct bilirubin, alkaline phosphatase, ALT, and AST
- Complete Blood Count (CBC) (for antimicrobial arm only)
- Blood draw for gene expression
- Buccal and fecal samples collection for microbial ecology

8.7 Eighteen (18) month phone contact

Approximately 18 months (visit window of 18 months +/- 4 weeks) after enrollment, all subjects will be contacted by the site coordinator to document the following:

- Vital status
- Medication adherence
- Hospitalization and respiratory infection information

